#### **Secondary objectives:**

- To assess the level of PpIX accumulation in AK lesions at treatment visits, in the absence or presence of neoadjuvant D3. (fluorescence dosimetry measurements)
- To assess tolerability of the technique. (Pain scale measurements)
- To assess patient satisfaction with the technique. (Cosmetic result, and questionnaire)
- To assess D3 serum levels (in serum) and VDR status (in leukocyte DNA), and to correlate these results to clinical outcomes.

Characteristics of the above parameters will be summarized as means and standard deviations (medians and quartiles) or percentages and frequencies. We will also compare the characteristics of screened and randomized patients using appropriate two-sample comparison procedures (t-test, Chi-squared test, etc.).

Analyses of study endpoints will follow the intention-to-treat (ITT) principle. For each relevant

endpoint, we will summarize its trajectories over study visits by randomization assignment for each patient. Linear mixed-effects models will be the primary analytic tools to analyze continuous endpoints by accounting for within-patient randomization, multiple lesions from the same patient and repeated measurements over time. The models will include fixed effects of treatment and visit and multiple random effects that represent the hierarchical data structure. Similarly, generalized linear mixed-effects models will be applied to categorical endpoints (binomial data, e.g., number of lesions with CR). The analysis for time to clearance will be based on a random-frailty survival model, where lesions without CR will be considered to have clearance times censored at the end of study. Further exploratory analyses will adjust these models by controlling for important initial parameters (e.g., initial tumor size).

All analyses will be conducted using SAS 9.3 (Cary, NC). Results will not be adjusted for multiple comparisons, and statistical significance will be established with a two-sided p-value < 0.05.

**Estimate of the accrual rate:** Patients who have been scheduled to receive PDT in our noninvasive cutaneous oncology clinics will be given written information prior to their visit, including a copy of the Informed Consent (IC) that describes the purpose of the study. If the patient indicates that he/she is interested, the physician or study nurse will review the IC with the patient on the day of PDT and answer all questions. We estimate an enrollment of 1 patient each week.

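### Section 14.0 plans a time-to-clearance frailty model, but lesions are counted only once after PDT, so clearance times are not observed; its randomisation terms also need relabelling.

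*Combined protocol and SAP*

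**What the plan says.** Section 14.0 (Secondary objectives) specifies a survival analysis at lesion level: "The analysis for time to clearance will be based on a random-frailty survival model". The only timing rule is for lesions that do not clear: "lesions without CR will be considered to have clearance times censored at the end of study". The plan neither defines the end of study nor says what time a cleared lesion receives.

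The data it would draw on are set elsewhere:
- Section 12.2.1 takes the response from counts at Visit 2 (the PDT day) and Visit 3.
- The Section 11.6 calendar has no other skin examination after PDT, only a side-effect phone call at 24-48 hours. Visit 3 may fall anywhere from 3 to 6 months after Visit 2.
- Section 6.3 plans no formal follow-up after that. It encourages routine visits at 6-month intervals, at which further standard care may be given.

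The same part of Section 14.0 uses randomisation terms: "We will also compare the characteristics of screened and randomized patients"; "we will summarize its trajectories over study visits by randomization assignment for each patient"; and models "accounting for within-patient randomization, multiple lesions from the same patient and repeated measurements over time". Section 3.1 describes a non-randomised comparison with a cohort from a previous study, and Section 5.3 says nothing is randomised.

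**The concern.** A survival model needs to know when each lesion cleared. One look after treatment shows only whether it had cleared by that look. The natural way to run the model is to use the Visit 3 date as the event time, but that date reflects scheduling, not biology. The controls come from an earlier study, and a shared 3-6 month window does not make the two sets of dates equal within it.

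If the D3 cohort was seen earlier on average, its lesions appear to clear faster; if later, a real benefit is hidden or reversed. Section 14.0 tests at two-sided p < 0.05 without multiplicity adjustment, so a hazard ratio produced by visit timing could be reported as a clearance benefit.

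The randomisation terms are a smaller matter. They describe a design this trial does not have.

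**Working it through.** **The plan's own figure.** Section 14.0 gives one design calculation, for the primary paired t-test: 70% v 90%, SD 24%, correlation 0.1, two-sided alpha 0.05, 90% power.
- SD of the paired difference = 24 × √(2 × (1 − 0.1)) = 32.2.
- Normal approximation: n = ((1.960 + 1.282) × 32.2 / 20)² = 27.2, so 28.
- Noncentral t: power 89.8% at n = 29 and 90.8% at n = 30.

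The stated 30 reproduces. It does not depend on time to clearance.

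**What the model does with one look.** Take 30 patients per cohort with 12 lesions each (an assumption; eligibility is more than 10), so 30 × 12 = 360 lesions per cohort. At 70% clearance, 252 clear and 108 do not. Use a proportional hazards model with Breslow ties and no frailty, so that the algebra is visible; θ is the hazard ratio, D3 over control.

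1. *Nominal month 3 for everyone.* All events tie at one time with everyone at risk. The score equation gives θ = (proportion cleared, D3) / (proportion cleared, control). With 70% in both, θ = 1; with 90% v 70%, θ = 0.90 / 0.70 = 1.29. The model repeats the proportions.
2. *Actual dates, no true effect, uncleared lesions censored at month 6.* Put all D3 visits at 3.5 months and all control visits at 4.0. At 3.5 the risk set is 360 v 360, with 252 D3 events. At 4.0 it is 108 v 360, with 252 control events. The score equation is 1 = θ/(θ + 1) + 0.3θ/(0.3θ + 1), which reduces to θ² = 1/0.3, so θ = 1.83 with identical clearance. Reversing the dates gives 1/1.83 = 0.55.
3. *Same dates, uncleared lesions censored at their own visit.* At 4.0 only controls remain at risk, so that time carries no comparison. At 3.5 every event is in the D3 cohort, and θ has no finite estimate.
4. *True 90% v 70%, D3 seen later (4.0 v 3.5), month-6 censoring.* D3 events are 0.90 × 360 = 324. The score equation is 324 = 252θ/(θ + 1) + 324θ/(θ + 0.3), or 252θ² − 21.6θ − 97.2 = 0, so θ = 0.67. The true benefit appears as harm.

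**With spread in the dates.** These are simulations with 30 v 30 patients, 12 lesions each and 70% clearance in both cohorts. The patient SD was 23-24%, close to the plan's 24%. Mean dates were assumed, with a moderate spread within the window. The model is a cluster-robust Cox as a stand-in for the frailty model, 150 runs per row.

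| Mean Visit 3, D3 v control (months) | Month-6 censoring | Own-visit censoring |
|---|---|---|
| 4.0 v 4.0 | HR 0.98, 9% rejected | HR 0.97, 7% |
| 3.5 v 3.75 | HR 1.22, 21% | HR 1.79, 55% |
| 3.5 v 4.0 | HR 1.45, 62% | HR 2.88, 97% |

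A separate simulation of the last row gave HR 1.4 with 53%, and HR 3.3 with 98%. A t-test on each patient's proportion cleared rejected in 3-9% of the null runs.

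An actual lognormal frailty fit with month-6 censoring, over date SDs of 0.2 to 0.7 month, rejected in 3-5% of runs at 4.0 v 4.0. At 3.5 v 4.0 it gave HR 1.42-1.97 and rejected in 29-85%.

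**The case against.** **The plan does not say that the appointment date is the event time.** This stands. A reader might infer that the model as written must be biased, but Section 14.0 gives a censoring rule and no event-time rule. Sections 6.0 and 11.5 label Visit 3 as month 3. Under nominal time no date difference can enter, and the model is redundant rather than biased (case 1 above). What the text supports is that clearance times are not observed and the event time is undefined.

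**Nothing shows that the cohorts' dates differ.** This also stands. The calendar sets the window to match the control study, and neither cohort's dates are given. The rates above show sensitivity and do not forecast bias.

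**The largest rates do not come from the planned model.** True: they come from a Cox model with own-visit censoring. When a lognormal frailty model was fitted that way with dates in days, it returned no p-value in 40 of 40 runs, so under that reading it would fail visibly. The month-6 frailty results show the effect in the planned type of model.

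**Later routine visits might supply times.** They do not. They are outside formal follow-up, come after the endpoint visit and may include further treatment.

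**The randomisation wording might seem to leave the comparison undefined.** The documents do not support that reading. Sections 3.1 and 14.0 (Primary objective) define the two groups, and the secondary text itself compares PpIX "in the absence or presence of neoadjuvant D3" and states: "The models will include fixed effects of treatment and visit".

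**Conclusion.** The point holds as a defect in one secondary analysis. With a single count after PDT, time to clearance is not observed, the event time and the end of study are undefined, and the model either restates the proportion cleared or picks up visit timing. This follows from Sections 6.3, 11.6, 12.2.1 and 14.0 without simulation.

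The size depends on dates that the documents do not give. Under the assumptions above, equal mean dates leave error rates near nominal. A half-month difference gives roughly 50-60% false positives at HR about 1.4 (month-6 censoring), or over 95% at HR about 3 (own-visit censoring), using the Cox stand-in.

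A reader might take this as a threat to the main result. It is not: the paired t-test on percent reduction and its 30 patients are untouched, as are the PpIX models and the binomial clearance model once labelled by cohort. Time to clearance appears in none of the stated objectives. The randomisation terms contradict Sections 3.1 and 5.3 and need relabelling only.

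**What to change.** 1. Delete the time-to-clearance sentence and its censoring rule from Section 14.0.
2. Analyse clearance at Visit 3 with the model already in that section, where "generalized linear mixed-effects models will be applied to categorical endpoints (binomial data, e.g., number of lesions with CR"). Specify cohort as the comparison and a patient random effect. This requires that lesions mapped at Visit 2 are re-identified at Visit 3 in both cohorts; Section 6.0 maps them at Visit 2 but only counts and photographs them at Visit 3. If they are not re-identified, use patient-level percent reduction.
3. Tabulate months from PDT to Visit 3 by cohort, and adjust for months since PDT as a sensitivity analysis only.
4. Replace the three randomisation phrases with cohort and matched-pair terms, to agree with Sections 3.1, 5.3 and 14.0 (Primary objective).

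The cost is protocol and SAP wording, with no added patients or visits. One analysis is lost, and it serves no listed objective.

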## APPENDIX I

### APPENDIX 1. DNA EXTRACTION FROM WHOLE BLOOD

[name] 5-Nov-2011, from [name] (technologist in [name] lab in Pathobiology)  
Notes on blood sample handling for R21 Efudex/PDT study

#### OVERVIEW:

1. Collect blood from patient in lavender top 10 ml Vacutainer tube, with EDTA.
2. The blood should stay at room temperature; do NOT put on ice (which activates platelets)
3. The blood must undergo the first processing step (RBC lysis and centrifuge spin) within 24 hr after collection. After that, the WBC pellet can stay at room temp in the cell lysis buffer for weeks to months before processing and collection of the DNA.

#### REAGENTS TO PURCHASE:

You'll need 3 Genra Puregene kit components from Qiagen, plus standard alcohols:

• RBC Lysis solution (Qiagen Cat# 158904)
• Cell Lysis buffer (Qiagen Cat# 158908)
• Protein Precipitation solution (Qiagen Cat# 158912)
100% isopropanol (2-propanol)
70% ethanol
Tris-EDTA, pH 8 (warmed to 60 °C)

#### OTHER SUPPLIES NEEDED:

50 ml conical tubes	Large table-top centrifuge
15 ml tubes, and tube rack	Ice bucket
5 ml and 10 ml plastic pipettes	Timer
Pipet-Aid	Alcohol resistant pen (VWR Lab Marker)
1000 µl Pipetman and tips	Labels
	Gloves, disposable (wear at every step)

#### STEPS PRIOR TO DNA EXTRACTION: (Wear mask, or work behind glass in hood)

1. Label a 50 ml conical tube with blood specimen ID, and fill the tube with the following volume of RBC lysis solution:  
For 9 ml of blood, use 27 ml of lysis solution  
If < 6 ml of blood, use 18 ml  
If > 9 ml of blood, use 30 ml
2. Invert the blood specimen to mix; then transfer the blood to 50 mL tube with the lysis solution.
3. Incubate tubes for 5 min at room temp; gently invert the tubes 3x's during the 5 min period
4. Centrifuge at 2,000 x g (RCF) for 5 min.

5. Carefully pipet off the supernatant with a 25 mL pipet, into a spare 50 ml conical tube, retaining the white cell (WBC) pellet. Leave ~ 200µl on the pellet. (Be sure to cap the waste tube tightly dispose in Biohazard)
6. Resuspend the pellet by Vortexing 10 sec.
7. Add 12 ml Cell Lysis Buffer to the pellet. Vortex for 20 sec. This lyses the cells and precipitates the proteins. [The tube can be stored at room temp for months, up to 2 years.]

-----  
DNA EXTRACTION:

8. Add 4 ml Protein Precipitation Solution to the 12 ml of lysate. Shake vigorously for 20 sec.
9. Centrifuge at 2,000 x g for 5 min. After centrifugation, the precipitated proteins should form a tight, dark brown pellet. If the supernatant is not clear, or if pellet is not tight, vortex again and incubate 5 min on ice. Then repeat centrifugation. (*[name] not too strict about the clarity aspect; still gets good result even if slightly brown*).
10. Add 12 ml of 100% Isopropanol to a labeled 50 ml conical tube.
11. Pour supernatant from Step 9 into the Isopropanol tube. Mix the sample by gently inverting 50 times. Centrifuge at 2,000 x g for 3 min.
12. Pour off supernatant into waste, watching the pellet carefully. Briefly drain the tube on absorbent paper.
13. Add 12 ml of 70% ethanol to the 50 ml tube. Shake the tube to wash the pellet. Centrifuge at 2,000 x g for 1 min.
14. Pour off supernatant into waste, watching the pellet carefully. If pellet slides, roll tube as you drain. Briefly drain the tube on absorbent paper. Let air dry for 5-15 min after carefully wiping tube with a fresh, clean Kimwipe. (*Do not overdry, or cannot re-dissolve the DNA.*)
15. Using the 1000 µl pipetter and disposable tip, add 400 µl Tris-EDTA (warmed to 60 °C) to the 50 ml tube. Run the tube along a microtube rack to mix.
16. Incubate in a 60 °C waterbath for 1 hr. Transfer the DNA into a labeled 1.5 ml tube with cryo label. Samples may be stored at 4 °C for short period, and at -20 °C for long-term storage.
